7.2 Interim Analysis

There was no planned interim analysis for this study.

7.3 Efficacy Assessments

7.3.1 mJSW

Radiographs of the knee joints were to be taken at all clinic visits after Visit 1E (Day 1).

Radiographs were to be taken using a posterior-anterior view.

Upon receipt of images, the central imaging vendor was to assess the image quality as acceptable or unacceptable. It was recommended that the Investigator attempt up to 3 additional image captures in order to obtain an acceptable image. mJSW measurements will be reported to two decimal places.

7.3.2 Pain NRS

The Pain NRS is an 11-point scale [0-10] for subject self-reporting of average knee pain in the previous 24 hours, where 0 represents no pain and 10 represents extreme pain. A pain NRS assessment was to be completed by the subjects at all clinic visits. Upon completion of the pain NRS, subjects were to sign or initial, then date the source document to indicate that the assessment is reported accurately.

7.3.3 WOMAC

The WOMAC is a widely used, proprietary outcome measurement tool used by health professionals to evaluate the condition of patients with OA of the knee and hip, including pain, stiffness, and physical functioning of a target joint. The WOMAC Version NRS 3.1 was to be

completed by the subject for their target knee at all clinic visits after Visit 1E (Day 1). Upon completion of the WOMAC, subjects were to sign or initial, then date the source document to indicate that the assessment is reported accurately.

WOMAC consists of 24 questions in three domains: physical function (17 questions), pain (5 questions) and stiffness (2 questions). The response for each question in the NRS format ranges from 0 to 10. Each domain subscore as well as a total score are calculated by adding together the numerical responses for a range of 0 to 240 total points. For analysis, WOMAC scores will be linearly transformed to a 0-100 scale, where 0 represents no difficulty and 100 represents extreme difficulty.

7.3.4 Patient Acceptable Symptom State Questionnaire

The Patient Acceptable Symptom State (PASS) Questionnaire consists of a single question “Taking into account all the activities you have during your daily life, your level of pain, and also your functional impairment, do you consider that your current state is satisfactory?” Subjects were asked to choose the answers of “Yes” or “No”. The PASS Questionnaire was to be completed by the subject at Visit 1E (Day 1), Visit 3E (Week 48), every 52 weeks thereafter (e.g., Visits 6E, 8E, etc.), and at the Termination Visit. Upon completion of the PASS Questionnaire, subjects were to sign or initial, then date the source document to indicate that the assessment is reported accurately.

7.3.5 SF-36

The SF-36 is a widely used questionnaire that relies upon subject self-reporting to measure the subject’s HRQOL. The SF-36 was to be completed by the subject at Visit 3E (Week 48), every 52 weeks thereafter (e.g., Visits 6E, 8E, etc.), and at the Termination Visit. The subject’s responses will be used to calculate norm-based scores for eight scales (physical functioning, role-physical, bodily pain, general health, vitality, social functioning, role-emotional, mental health) and two component summary measures (physical health, mental health). Scoring software provided by the SF-36 vendor, Optum, will be utilized to calculate the standardized scores.

7.3.6 NSAID/Acetaminophen Usage

Information about NSAID and acetaminophen usage was collected at all clinic visits after Visit 1E (Day 1). Subjects were asked to recall the name, indication, route of administration, usual total daily dose, and usual number of days taken per week of any NSAID or acetaminophen medications during the previous 4 weeks. Assessment of NSAID/acetaminophen usage will be documented on the “NSAID/Acetaminophen Usage” eCRF.

7.4 Safety Assessments

7.4.1 Adverse Events

An AE is any unfavorable and unintended sign, symptom, or disease temporally associated with the use of an IP or other protocol-imposed intervention, regardless of attribution. Signs and symptoms of exacerbation or worsening of target knee OA were captured in the context of efficacy assessments. Anticipated fluctuations or anticipated deterioration (in the opinion of the Investigator) of the underlying disease (target knee OA) were not considered as AEs.

Severity was assessed utilizing the CDISC AESEV, which classifies AEs as mild, moderate, or severe. For analysis, relationship will be dichotomized into Unrelated (combining Not Related and Unlikely Related) and Related (combining Possibly Related and Probably Related).

7.4.2 Vital Signs and Weight

Vital signs were measured by a qualified staff member at Visit 2E, Visit 3E, every 52 weeks thereafter (e.g., Visits 6E, 8E, etc.), and at the Termination Visit. At each time point, the following vital signs were measured:

- Pulse rate
- Blood pressure (systolic and diastolic) after the subject rests (sitting or supine) for at least 5 minutes

At visits when the subject received an IA injection (e.g., Visits 3E, 6E, 8E, etc.), temperature was also measured.

Any measurement that was, in the opinion of the Investigator, abnormal AND clinically significant was to be recorded as an AE.

Weight measurements were taken at Visit 2E, Visit 3E, every 52 weeks thereafter (e.g., Visits 6E, 8E, etc.), and at the Termination Visit.

7.4.3 Clinical Laboratory Evaluations

Specimens for clinical laboratory analysis were to be collected at Visit 2E, Visit 3E, every 52 weeks thereafter (e.g., Visits 6E, 8E, etc.), and at the Termination Visit. Subjects were asked to fast prior to the Visit 3E clinical laboratory collection. At a minimum, the following tests were conducted:

- **Chemistry panel:** Albumin, alkaline phosphatase (ALP), alanine aminotransferase (ALT), aspartate aminotransferase (AST), blood urea nitrogen, bicarbonate, calcium, calcium (corrected total), chloride, creatinine, glucose, lactate dehydrogenase (LDH), potassium, sodium, bilirubin (total)
- **Hematology:** Hemoglobin, hematocrit, red blood cell (RBC) count, white blood cell (WBC) count with differential, and platelet count
- **Urinalysis:** Clarity, specific gravity, pH, protein, glucose, ketones, nitrite, leukocyte esterase, and occult blood

Urine microscopy was to be performed if urinalysis urine protein, leukocyte esterase (WBC esterase), occult blood, or nitrite values were out of range, or if the Investigator deemed that the microscopy was clinically warranted.

7.4.4 Biomarkers

Fasting blood samples for biomarker analysis were collected by a qualified staff member at Visit 3E. Biomarkers that were assessed include bone biomarkers, P1NP and β -CTX, and a cartilage biomarker, COMP.

8. STUDY SUBJECTS AND DEMOGRAPHICS

8.1 Disposition of Subjects and Withdrawals

Subject disposition will be presented in a summary table detailing the number and percentage of subjects who were consented, treated, or discontinued (e.g. study terminated by sponsor, adverse event, subject decision, etc.) overall and by treatment group. Additionally, subject disposition for treated subjects will be presented by treatment group and study site. Additional tables will be prepared to summarize the number of subjects enrolled under each protocol version and included in each analysis set. The disposition for individual subjects will be listed along with additional information on discontinued and screen failed subjects.

8.2 Protocol Deviations

A protocol deviation is defined as any noncompliance with the clinical trial protocol requirements. The noncompliance may be either on the part of the subject, the Investigator, or the study site staff.

Deviations are summarized into one of the following categories:

- Informed Consent Form
- Enrollment
- Procedures
- Labs/Specimens
- Study Visits
- Investigational Product
- Subject Non-Compliance
- Serious Adverse Events

Deviations are categorized as major or minor by a cross-functional team according to pre-defined criteria established in the Protocol Deviation Classification Guideline.

- A major deviation is defined as a divergence from the protocol that materially (a) reduces the quality or completeness of efficacy data, (b) makes the informed consent inaccurate, or (c) impacts a subject's safety, rights or welfare.
- A minor deviation is defined as a divergence from the protocol that deviates from the procedures and guidelines outlined in the protocol, but is not classified as a major deviation (i.e. the deviation does not materially (a) reduce the quality or completeness of the data, (b) make the informed consent inaccurate, or (c) impact a subject's safety, rights or welfare).

Protocol deviations may result in subject exclusion from the PPAS. All protocol deviations were reviewed by study team members to determine if the deviation could reasonably affect/confound interpretation of key efficacy endpoints and should result in the subject being excluded from the PPAS. 27 subjects (29 protocol deviations) with the following types of deviations were excluded from PPAS:

- Major parent study protocol deviation impacting efficacy outcome(s):

- Major EN01 deviations (subject randomized or enrolled without meeting eligibility criteria): n = 3
- Major NC03 deviations (prohibited procedure done): n = 2
- Major OA-07 study protocol deviation impacting efficacy outcome(s):
 - Major NC03 deviations (prohibited procedure done): n = 1
 - Major NC04 deviations (prohibited concomitant medication taken) that would affect efficacy analysis at Visit 3E (Week 48) or Visit 6E (Week 100): n = 5
 - Major P01 deviations (procedure performed incorrectly): n = 5
 - Major P02 deviations (Procedure not attempted or not performed): n = 13

A final list of protocol deviations resulting in subject or data exclusion from the PPAS can be found in Appendix 1 – Protocol Deviations Leading to Exclusion from Per-Protocol Analysis.

Major protocol deviations will be summarized by site and category, and all protocol deviations will be listed for each subject. Additionally, the COVID-19 pandemic related protocol deviations will be summarized separately.

8.3 Demographics and Other Baseline Characteristics

Demographic and parent-study baseline characteristics, including sex, race, ethnicity, age at consent, weight, height, body mass index (BMI), Kellgren-Lawrence (KL) grade, Widespread Pain Index (WPI), Symptom Severity Question 2 (SSQ2), mJSW, and investigator-assessed OA laterality will be presented overall and by treatment group. Continuous variables will be summarized with descriptive statistics and categorical variables will be summarized with frequencies and percentages. Summaries will be provided for each analysis set. Subject level listings will also be provided.

8.4 Medical History

A summary of reported medical history will be provided by MedDRA system organ class on the Safety Analysis Set for each treatment group. A subject-level listing will provide further information on each event.

9. EFFICACY ANALYSIS

9.1 Hypothesis Testing using Parent-Study (OA-11 Study) Baseline

The primary and secondary statistical hypotheses being tested, using parent-study baseline, in this study are:

1. The least squares estimate of improvement from parent-study baseline in medial joint space width in the target knee at Visit 3E (Week 48) is greater for subjects who received LOR compared to placebo.
2. The least squares estimate of improvement from parent-study baseline in Pain NRS at Visit 3E (Week 48) is greater for subjects who received LOR compared to placebo.
3. The least squares estimate of improvement from parent-study baseline in WOMAC Pain at Visit 3E (Week 48) is greater for subjects who received LOR compared to placebo.

4. The least squares estimate of improvement from parent-study baseline in WOMAC Function at Visit 3E (Week 48) is greater for subjects who received LOR compared to placebo.
5. The least squares estimate of improvement from parent-study baseline in Pain NRS at Visit 2E (Week 24) is greater for subjects who received LOR compared to placebo.
6. The least squares estimate of improvement from parent-study baseline in WOMAC Pain at Visit 2E (Week 24) is greater for subjects who received LOR compared to placebo.
7. The least squares estimate of improvement from parent-study baseline in WOMAC Function at Visit 2E (Week 24) is greater for subjects who received LOR compared to placebo.

Other statistical hypotheses being tested, using parent-study baseline, in this study are:

1. The least squares estimate of improvement from parent-study baseline in medial joint space width in the target knee at Visit 2E (Week 24) is greater for subjects who received LOR compared to placebo.
2. The least squares estimate of improvement from parent-study baseline in WOMAC Total score at Visit 3E (Week 48) is greater for subjects who received LOR compared to placebo.
3. The least squares estimate of improvement from parent-study baseline in WOMAC Stiffness at Visit 3E (Week 48) is greater for subjects who received LOR compared to placebo.
4. The least squares estimate of improvement from parent-study baseline in WOMAC Total score at Visit 2E (Week 24) is greater for subjects who received LOR compared to placebo.
5. The least squares estimate of improvement from parent-study baseline in WOMAC Stiffness at Visit 2E (Week 24) is greater for subjects who received LOR compared to placebo.
6. The least squares estimate of improvement from parent-study baseline in medial joint space width in the target knee at Visit 6E (Week 100) is greater for subjects who received “Placebo-LOR”, “LOR-LOR” and All (pooled “Placebo-LOR” and “LOR-LOR”) subjects compared to test values (carry forward and progression assumptions) derived from the change from baseline estimates from the Placebo group at Visit 3E (Week 48)

9.2 Hypothesis Testing using OA-07-Study Baseline

The secondary statistical hypotheses being tested, using OA-07-study baseline, in this study are:

1. The least squares estimate of improvement from OA-07-study baseline in medial joint space width in the target knee at Visit 3E (Week 48) is greater for subjects who received LOR compared to placebo.
2. The least squares estimate of improvement from OA-07-study baseline in Pain NRS at Visit 3E (Week 48) is greater for subjects who received LOR compared to placebo.
3. The least squares estimate of improvement from OA-07-study baseline in WOMAC Pain at Visit 3E (Week 48) is greater for subjects who received LOR compared to placebo.

4. The least squares estimate of improvement from OA-07-study baseline in WOMAC Function at Visit 3E (Week 48) is greater for subjects who received LOR compared to placebo.
5. The least squares estimate of improvement from OA-07-study baseline in Pain NRS at Visit 2E (Week 24) is greater for subjects who received LOR compared to placebo.
6. The least squares estimate of improvement from OA-07-study baseline in WOMAC Pain at Visit 2E (Week 24) is greater for subjects who received LOR compared to placebo.
7. The least squares estimate of improvement from OA-07-study baseline in WOMAC Function at Visit 2E (Week 24) is greater for subjects who received LOR compared to placebo.

Other statistical hypotheses being tested, using OA-07-study baseline, in this study are:

1. The least squares estimate of improvement from OA-07-study baseline in medial joint space width in the target knee at Visit 2E (Week 24) is greater for subjects who received LOR compared to placebo.
2. The least squares estimate of improvement from OA-07-study baseline in WOMAC Total score at Visit 3E (Week 48) is greater for subjects who received LOR compared to placebo.
3. The least squares estimate of improvement from OA-07-study baseline in WOMAC Stiffness at Visit 3E (Week 48) is greater for subjects who received LOR compared to placebo.
4. The least squares estimate of improvement from OA-07-study baseline in WOMAC Total score at Visit 2E (Week 24) is greater for subjects who received LOR compared to placebo.
5. The least squares estimate of improvement from OA-07-study baseline in WOMAC Stiffness at Visit 2E (Week 24) is greater for subjects who received LOR compared to placebo.
6. The least squares estimate of improvement from OA-07-study baseline in medial joint space width in the target knee at Visit 6E (Week 100) is greater for subjects who received “Placebo-LOR”, “LOR-LOR” and All (pooled “Placebo-LOR” and “LOR-LOR”) subjects compared to test values (carry forward and progression assumptions) derived from the change from baseline estimates from the Placebo group at Visit 3E (Week 48)

9.3 Estimands

The primary estimand for this trial is the difference between an additional injection of LOR versus placebo in mean parent-study baseline-adjusted change in medial joint space width in the target knee at Visit 3E (Week 48) analyzed with parent-study baseline-adjusted ANCOVA in the FAS.

A summary of all estimands defined for this study is available in Appendix 2 – Estimands.

9.4 Primary Efficacy Analysis

9.4.1 Main Analysis

Parent-study baseline-adjusted ANCOVA will be used to assess the change in mJSW at Visit 3E (Week 48) in the FAS.

9.4.2 Sensitivity Analysis

Missing data will be imputed using the MI method as described in Section 7.1.4. The main primary analysis will also be repeated for subjects in the mFAS, CAS, and PPAS.

9.5 Secondary Efficacy Analysis

9.5.1 Main Analysis

Parent-study baseline-adjusted and OA-07-study baseline-adjusted ANCOVA will be used to assess the change in Pain NRS, WOMAC Pain, and WOMAC Function at Visit 2E (Week 24) and Visit 3E (Week 48) in the FAS. Additionally, the OA-07-study baseline-adjusted ANCOVA will be used to assess the change mJSW at Visit 3E (Week 48) in the FAS.

9.5.2 Sensitivity Analysis

Missing data will be imputed using the MI method as described in Section 7.1.4. The main secondary analyses will also be repeated for subjects in the mFAS, CAS, and PPAS.

9.6 Other Efficacy Analysis

The analyses described below will be performed on subjects in the FAS, mFAS, CAS, and PPAS.

9.6.1 Using Parent-Study Baseline

Parent-study Baseline-adjusted ANCOVA will be used to assess change in mJSW (at Visit 2E), WOMAC Total (at Visit 2E and Visit 3E), WOMAC Stiffness (at Visit 2E and Visit 3E), and in SF-36 (at Visit 3E). Unadjusted 95% confidence intervals and P values will be reported.

9.6.2 Using OA-07-Study Baseline

OA-07-study baseline-adjusted ANCOVA will be used to assess the change in mJSW (at Visit 2E), WOMAC Total (at Visit 2E and Visit 3E), WOMAC Stiffness (at Visit 2E and Visit 3E), and in SF-36 (at Visit 3E).

9.6.3 PASS and Response Analysis

The number and percent of subjects reporting “Yes” to Patient Acceptable Symptom State (PASS) at Visit 3E (Week 48) and Visit 6E (Week 100) will be summarized. Logistic regression analysis will be implemented for “Yes” responses in PASS adjusted for their response at Visit 1E (Day 1), with 95% confidence intervals and P values reported.

The number and percent of subjects reporting Outcome Measures in Rheumatology Clinical Trials (OMERACT)-Osteoarthritis Research Society International (OARSI) ‘strict’ responders will be summarized. An OMERACT-OARSI ‘strict’ responder must have a 50% improvement with corresponding 20 point (out of 100) actual scale improvement in pain or function outcomes. Two ‘strict’ responder outcomes will be estimated, one using WOMAC Pain and WOMAC Function and the other using Pain NRS (2-point improvement out of 10) and WOMAC Function.

Additionally, the number and percent of subjects reporting 20% improvement, 30% improvement, 50% improvement, and 70% improvement in Pain NRS, WOMAC Pain, and WOMAC Function will be summarized. Logistic regression analysis will be implemented for improvement in these assessments as well, with 95% confidence intervals and P values reported.

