10.2 STATISTICAL HYPOTHESES

The statistical hypotheses being tested in this study are: the least squares estimate of improvement from parent-study baseline in clinical and radiographic outcomes at Visit 3E (i.e., after 24 months of treatment) is greater for subjects who received LOR compared to those who received placebo. Details of the statistical hypothesis tests will be outlined in the SAP.

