10.4.3 ANALYSIS OF EFFICACY ENDPOINT(S)

Change over time through Visit 3E in mJSW, pain NRS, WOMAC Pain, WOMAC Function, and WOMAC Total will be characterized using mixed-effects models for repeated measures (MMRM). The models will estimate change from parent-study baseline with treatment, visit, treatment \times visit interaction, and parent-study baseline value as covariates. Unadjusted 95% confidence intervals and *P* values will be reported. The potential confounding effect of change in NSAID/acetaminophen usage on the treatment effect will be considered for sensitivity analysis.

ANCOVA will be used to analyze the change in SF-36 domain scores and summary component scores through Visit 3E. Change will be assessed from parent-study baseline between the active and placebo treatment groups. The models will be adjusted for parent-study baseline. Unadjusted 95% confidence intervals and *P* values will be reported.

PASS will be analyzed using logistic regression. Logistic regression will also be used to compare the proportion of Outcome Measures in Rheumatology Clinical Trials (OMERACT)-Osteoarthritis Research Society International (OARSI) responders and “strict” responders ([Pham et al. 2003](#)) between treatment groups through Visit 3E, as well as proportion of subjects achieving a 20%, 50%, and 70% improvement.

Maintenance of LOR’s effects on pain and function of the target knee will be characterized by summarizing likelihood of response in pain NRS, WOMAC Pain, and WOMAC Function in the current study for those subjects that had a response in the parent study. Response will be characterized as a 20%, 50%, and 70% improvement.

After all subjects have received LOR at Visit 3E, all further efficacy analyses will be descriptive in nature.

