3.2.4 Other Endpoints

1. Change from parent-study and OA-07-study baseline in medial joint space width (mJSW) as documented by radiograph of the target knee at Visit 2E (Week 24)
2. Change from parent-study and OA-07-study baseline OA pain, function, and stiffness as a composite outcome measure as assessed by WOMAC Total score and Stiffness at Visit 2E (Week 24) and Visit 3E (Week 48)
3. Change from parent-study and OA-07-study baseline in mJSW, pain NRS, WOMAC Pain, and WOMAC Function at Visit 6E (Week 100) compared to test values (carry forward and progression assumptions) derived from the change from baseline estimates from the Placebo group at Visit 3E (Week 48)
4. Change from parent-study baseline health-related quality of life (HRQOL) as assessed by the 36-Item Short Form Health Survey (SF-36) at Visit 3E (Week 48)
5. Percentage of subjects who consider themselves to be in Patient Acceptable Symptom State (PASS) at Visit 3E (Week 48)

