4.3 Method of Treatment Assignment and Randomization

Subjects were randomized in the SM04690-OA-11 study. Each subject maintained the same treatment assignment of LOR or placebo as in the parent study at Visit 1E (Day 1). At Visit 3E

(Week 48) and for any subsequent injections until the Termination Visit, all subjects received LOR injection(s).

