4.4 Treatment Blinding

Subjects consented in this study were previously treated with an IA injection of either LOR or placebo in their target knee in the SM04690-OA-11 parent study that was double-blinded. The blind for the subject's previous treatment with either LOR or placebo will be maintained in this study for Investigators, site personnel, and subjects only. Sponsor was unblinded to treatment assignment once the database from the parent study was locked. At Visit 1E (Day 1), preparation of LOR or placebo for injection and the administration of the injections were to be performed by an Unblinded Investigator who had minimal contact with the subject for other aspects of the study. At Visit 3E (Week 48) and for any subsequent injections, the LOR injections did not need to be performed by a designated Unblinded Investigator due to the open-label nature of the remaining portion of the study.

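### The only planned PASS test conditions on the Visit 1E answer, given about a year into randomised treatment, so it does not compare the percentage in PASS at Visit 3E

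*SAP*

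**What the plan says.** SAP 3.2.4 lists the endpoint as "Percentage of subjects who consider themselves to be in Patient Acceptable Symptom State (PASS) at Visit 3E (Week 48"), which is a percentage at one visit and not a change since Visit 1E. SAP 9.6.3 summarises the number and percentage of Yes answers at Visits 3E and 6E, then plans logistic regression for Yes "responses in PASS adjusted for their response at Visit 1E (Day 1), with 95% confidence intervals and P values reported". SAP 9.6 repeats the analysis in the FAS, mFAS, CAS and PPAS, and SAP 9.6.6 repeats it by KL grade. None of these versions drops the Visit 1E covariate.

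On timing, SAP 4.3 states "Subjects were randomized in the SM04690-OA-11 study" and adds that each subject kept the parent-study arm at Visit 1E. SAP 4.4 confirms that everyone had already been injected with LOR or placebo. Protocol 7.3.1 places Visit 1E at the parent-study EOS visit (Week 56), with a window of +6 weeks.

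The protocol's general hypothesis, in Section 10.2, concerns improvement from parent-study baseline "at Visit 3E (i.e., after 24 months of treatment) is greater for subjects who received LOR compared to those who received placebo". For PASS itself, Protocol 10.4.3 says only "PASS will be analyzed using logistic regression".

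The other patient-reported outcomes have two views. SAP 9.5.1, 9.6.1 and 9.6.2 analyse pain NRS, the WOMAC scores and SF-36 from the parent-study baseline and also from the OA-07-study baseline.

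**The concern.** At Visit 1E a subject has had 56 to 62 weeks since entering randomised treatment, so the PASS answer there is an outcome of year 1. For the 24-month comparison it is not a baseline. Holding it fixed changes the question from whether the arms differ in the percentage in PASS at Visit 3E to whether they differ among subjects who gave the same answer at Visit 1E.

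Both questions are legitimate. The plan offers only the second for PASS, while the listed endpoint is the first. If LOR raised PASS in year 1 and held the gain, the reported odds ratio would understate the difference at Visit 3E. If the gain faded until the arms were equal, the report could show an odds ratio below 1 with a small P value beside two equal percentages.

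**Working it through.** **No figure to reproduce.** The documents give no PASS rate, effect size, alpha or power for PASS, and SAP 5 bases the roughly 500 subjects on practical considerations.

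**Assumptions, not in the documents:** 1:1 arms, 250 per arm with data, two-sided 5% Wald tests, placebo PASS 50% at both visits. The pair of answers follows a latent bivariate normal with correlation 0.5, 0.7 or 0.85, which gives phi = 0.33, 0.49 or 0.65 in the placebo arm.

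**Step 1: the two quantities differ.** Let a be the probability of Yes at Visit 3E after Yes at Visit 1E, and b the probability of Yes after No. Then P(Yes at 3E) = b + (a − b) × P(Yes at 1E). Take a = 0.90 and b = 0.15 in both arms, with Visit 1E at 60% (LOR) and 50% (placebo):
- LOR at 3E: 0.15 + 0.75 × 0.60 = 0.600
- Placebo at 3E: 0.15 + 0.75 × 0.50 = 0.525

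The arms differ by 7.5 points at Visit 3E, yet the adjusted odds ratio is 1. In simulation (4,000 trials) the planned test rejected in 4% and the test without the covariate in 41%.

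**Step 2: sustained benefit, 50% vs 62% at both visits.** Without the covariate:
- log OR = ln[(0.62/0.38)/(0.50/0.50)] = 0.490, so OR = 1.63
- SE = √{(1/250)[1/(0.50 × 0.50) + 1/(0.62 × 0.38)]} = 0.182
- power = Φ(0.490/0.182 − 1.96) = 0.77

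For the planned model, the logistic regression was fitted to the expected cell counts, with power = Φ(log OR/SE − 1.96):

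| phi | adjusted OR | log OR | SE | power |
|---|---|---|---|---|
| 0.33 | 1.44 | 0.367 | 0.193 | 0.48 |
| 0.49 | 1.39 | 0.328 | 0.209 | 0.35 |
| 0.65 | 1.35 | 0.297 | 0.238 | 0.24 |

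The share of the log odds ratio that remains is 0.367/0.490 = 75% down to 0.297/0.490 = 61%.

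**Step 3: other patterns, 250 per arm.** Ranges run from phi 0.33 to 0.65; rejection is two-sided.

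| Pattern (placebo vs LOR) | Without covariate | Planned model |
|---|---|---|
| 1E 50 vs 62%, 3E 50 vs 50% | 0.05 | 0.16, 0.32, 0.59 (OR 0.83 to 0.59) |
| 1E 50 vs 55%, 3E 50 vs 50% | 0.05 | 0.07 to 0.16 |
| 50 vs 55% at both visits | 0.20 | 0.12 to 0.08 |
| 1E 50 vs 50%, 3E 50 vs 62% | 0.77 | 0.81 to 0.93 |
| 50 vs 50% at both visits | 0.05 | 0.05 |

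In the first two rows nearly all rejections are against LOR.

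**Step 4: sensitivity.** With 200 per arm, the sustained 50% vs 62% case gives 0.67 without the covariate and 0.40, 0.29 and 0.20 with it. Simulating a sustained 50% vs 60% at 250 per arm, with phi 0.3, 0.5 and 0.7, gives about 0.62 against 0.37, 0.24 and 0.14. The sizes move with the assumptions; the direction does not.

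**The case against.** The planned model answers a question the SAP asks. The objective includes a second year of use, SAP 9.3 words the primary estimand as the effect of an additional injection, and the Visit 1E answer is the OA-07-study baseline for PASS as SAP 7.1.1 defines it. For an effect arising only in year 2 the planned model is the more powerful one. This stands, and it is why the model should be kept. It does not supply the 24-month view that the other patient-reported outcomes have.

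The raw percentages will be tabulated, so a reader could see a sustained or faded difference and work out a crude interval. This also stands, but the only reported P value and interval would answer another question.

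Four stronger readings are tempting and are not supported:
- **The test breaks its type I error.** No null for PASS is written. Protocol 10.2 uses least-squares wording suited to continuous outcomes, and the hypothesis lists in SAP 9.1 and 9.2 omit PASS. In the fading case the model detects a real difference in its own conditional terms.
- **A sustained benefit is adjusted away.** In the 50% vs 62% case, 61-75% of the log odds ratio remains.
- **The covariate is an undeclared departure from the protocol.** Protocol 10.1 describes analyses in general terms and leaves the detail to the SAP, so naming a covariate is added detail and not clearly a change that SAP 13 had to list.
- **Dropping the covariate restores a randomised comparison.** The FAS contains only subjects who completed OA-11, enrolled and were injected in OA-07. That selection follows randomisation and affects both models.

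**Conclusion.** The point holds as a missing analysis. The single PASS test is conditional on a post-treatment answer, while the listed endpoint is the percentage at Visit 3E. Where the arms already differ at Visit 1E, the odds ratio and P value can mislead about that endpoint: power falls from about 0.77 to 0.48-0.24 for a sustained 12-point benefit, and 16-59% of trials reject against LOR when such a benefit fades to equality. With a Visit 1E gap of 5 points the latter figure is 7-16%. All of this rests on assumed PASS rates, correlations and arm sizes. If LOR has no effect at either visit, nothing is distorted.

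SAP 9.6.3 names neither the treatment term nor the visit for the regression, so the exact model is partly inferred. Visit 3E is the only visit with a placebo comparison, because every subject is due to receive LOR from then on. The stakes are limited: PASS is an 'other' endpoint, and pain NRS and WOMAC carry the symptom question on both baselines.

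**What to change.** In SAP 9.6.3:
- Add a Visit 3E comparison of LOR with placebo in PASS without the Visit 1E response, using treatment alone or treatment with pre-randomisation covariates already held, such as parent-study-baseline pain NRS and WOMAC Function. The documents do not say whether PASS was collected at parent-study baseline, and the fix does not need it.
- Report the difference in percentages with its 95% CI, and use this analysis for the 24-month question.
- Keep the Visit 1E-adjusted model as the OA-07-baseline, second-year analysis, labelled as conditional on status after year 1.
- Name the treatment term and the visit for each model.
- Note that both analyses are in subjects who completed OA-11 and enrolled in OA-07, so neither is a fully randomised comparison.

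SAP 4.4 says the sponsor was unblinded to allocation once the parent database was locked, so both models should be reported whatever they show. The cost is one extra model on data already collected and a few lines of SAP text. Nothing planned is lost.
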